**2.0 BACKGROUND**

**2.1 Describe the relevant prior experience and gaps in the current knowledge.**

Currently, several corporations are contracted with maxillofacial plating companies to provide 3D planning and printing of surgical models, stents, and guides to facilitate surgery. However, these services can be cost prohibitive and can require a considerable lead time. The typical minimum required time of 1 to 2 weeks for the planning and manufacturing process can be limiting when attempting to treat acute injuries in a timely fashion. On-site, or in-house, 3D model fabrication with preoperative plate bending is a cost- and time-effective option to provide predictable reconstructive solutions with an associated decrease in operative time and cost. An inexpensive on-site option mitigates the cost of an outside contracted biomedical engineering service, which has a typical per-case cost of \$1,000 to \$2,000, and decreases the time needed to deliver a patient-specific implant to the OR. [10]

Numerous types of 3D printers are currently commercially available, ranging from industrial machines costing more than \$100,000 to consumer-level products that yield nearly industrial-level results with start-up costs of under \$3,000. [10] The purpose of this study is to evaluate the feasibility, accuracy, and compatibility with current surgical approaches to re-work the current standards of care to include the use of on-site 3D model creation and preoperative plate bending for mandibular fractures.

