**4.1 Detail the investigators' experience as it pertains to the study.**

**4.0 INVESTIGATOR EXPERIENCE**

[name] has been a member of the UC Surgery faculty since 2008. He is currently associate professor of surgery and is serving as the chief of OMS at UC Medical Center and Cincinnati Children's Hospital. [name] obtained his dental degree from Bangalore University, India, and trained in Oral and Maxillofacial Surgery at Emory University's College of Medicine in Atlanta, Georgia. Upon completion of residency, [name] pursued further fellowship training in Oral & Maxillofacial Surgery focusing on orthognathic surgery at Dalhousie University, Halifax, Canada. He currently serves on the Committee of Education and Training (CET) of the AAOMS and is the chair of the special committee on Emerging leaders in OMS. He is also a consultant to the AAOMS Committee on Anesthesia (CAN) on Simulation in Anesthesia. [name] was in the first class of single degree oral and maxillofacial surgeons that were recognized as Fellows of the American College of Surgeons.

[name] is Vice Chair of Operations & Quality at the University of Cincinnati Department of Radiology, and he is the clinical lead for the 3D printing section at UCH. He is the past-Chair of the American College of Radiology Appropriateness Criteria, and the Founding Chair of the Radiological Society of North America 3D Printing Special Interest Group. He also is currently the Editor-in-Chief of the journal 3D Printing in Medicine. [name] obtained his medical

	
degree through the physician scientist program at Harvard -MIT (Medicine and Medical Engineering), and he completed his residency in Diagnostic Radiology at the Brigham and Women's Hospital and Harvard Medical School, Boston, MA.

5.0 STUDY ENDPOINTS	
	
5.1 Describe any primary and secondary study endpoints.
 
Outcome 1: Noninferiority of the clinical outcome (defined by OMS on the post-op, follow up exam approx. 6 weeks out) Based on physical exam
 
Outcome 2:
 
 
Total time in the OR
 
Time in the OR considered critical part of the procedure by the OMS Staff
 
 
Outcome 3
 
 
Subjective outcome to surgeon Likert scale
 
 
5.2 Describe any primary and secondary safety endpoints.
 
Not Applicable.

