	
6.1 Thoroughly describe the study design.
 
We plan to conduct a randomized controlled trial on trauma patients brought to either UCMC or UC HH OMS for treatment of isolated mandibular fractures. This study plans to elucidate whether the utilization of 3D models during operations where effective in minimizing both OR time and operational costs. Subjects will be identified based off the initial physical assessments made by surgical specialists from OMS, Plastic Surgery, and otolaryngology. Once the subjects are identified the research coordinator will conduct a screening of the patient to ensure they meet the inclusion/ exclusion criteria for the study and then randomize the patient into either normal standard of care for surgical repair of the fractured mandible or normal standard of care for surgical repair of the fractured mandible aided by a 3D printed model of the patient's jaw. Any chart reviewing will be conducted from existing electronic medical records maintained by UC Health EPIC and OMS Vision. All the following data would be based on the patient's condition at the time of surgery.

	
Following completion of the procedure, for the surgeons who received aide via the 3D model they will be asked to answer a brief Likert Scale survey outlining their thoughts how effectively or ineffectively the model assisted them. In addition to this information, if they feel the model increased efficiency saving time, they will be asked to state how much time they felt was saved. This time differential will be compared to current CPT codes for OR time to understand how much in operational costs were saved by utilizing the models.

6.0 PROCEDURES INVOLVED	

6.2 Detail the procedures being performed, specifically the interaction or intervention with human subjects and/or their identifiable information. Please be clear and concise and provide information relevant to the current study. For
	

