**TEMPLATE: RESEARCH PROTOCOL**

NUMBER	ACTIVE DATE	PAGE
HRP-503	02-04-2020	12 of 35

	
of a pregnancy test are negative or until delivery.) (HRP-412 MEMBER CHECKLIST Pregnant Women)
 
 Non-Viable Neonates (HRP-413 – MEMBER CHECKLIST Non-Viable Neonates)
 
 Uncertain Viability Neonates (HRP-414 – MEMBER CHECKLIST Uncertain Viability Neonates)
 
 Prisoners (HRP-415 – MEMBER CHECKLIST Prisoners)
 
10.4 If the research involves individuals listed in 10.3 or other individuals who are vulnerable to coercion or undue influence, please justify based on the applicable checklist and describe additional safeguards included to protect their rights and welfare.
 
N/A
 
10.5 If the research involves or may involve individuals who are students or employees where the research is taking place, please describe additional safeguards included to protect their rights and welfare.
 
Not Applicable

	
11.1 Indicate the total number of subjects to be accrued.
 
We aim to obtain 50 procedures for each arm of the study (100 in total)
 
50: standard surgical procedures aided by use of 3D Printed model
 
50: procedures carried out by standard surgical repair for isolated mandibular fractures (No model)

	
11.2 If applicable, distinguish between the number of subjects who are expected to be enrolled and screened, and the number of subjects needed to complete the research procedures.
 
N/A

	
12.1 Describe when, where, and how potential subjects will be recruited.
 
Subjects of this study are those that require emergent medical attention and are referred to either UCHMS Emergency Department or to UC OMS for treatment. Subjects will be triaged by the clinical providers, and the research coordinator will then complete a standardized informative process. Regardless of involvement, the subject will undergo the same treatment course as any other patient presenting with an isolated mandibular fracture. For the consenting of the surgical team members, they will undergo a research presentation given by the research coordinator in which they have an adequate amount of time to ask any questions or concerns before deciding to be a part of the study.

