**TEMPLATE: RESEARCH PROTOCOL**

NUMBER	ACTIVE DATE	PAGE
HRP-503	02-04-2020	18 of 35

	
of REDCap allows for close monitoring of data from the study supervisors. Additionally, only the research coordinator will have capability to add or remove data. REDCap allows the coordinator to designate or prevent specific rights to be assigned from team members.
 
17.4 Describe how data or specimens will be handled study wide as outlined below.
 
17.5 What information will be included in the data or associated with the specimens?
 
No specimens will be collected. The information collected will be as follows:
 
 
Procedural Time
 
Cost differential via model utilization
 
3D Printing Likert scale Questions answered by specialist post operatively
 

--	---

	
17.6 Who will have access to the data or specimens?
 
No specimens will be collected. Data access will be restricted to the research coordinator, the principal investigator, and co-investigators
 
17.7 Where and how data or specimens will be stored?
 
No specimens will be collected. As discussed earlier, all the data will be stored on REDCap.
 
17.8 How long the data or specimens will be stored?
 
No specimens will be collected. The data will be stored for the duration of the study, which is expected to take approximately two years, and for the duration of data analysis and peer-reviewed publication, which is expected to take another year. Realistically, the data will be stored for three years.
 
17.9 If applicable, how data or specimens will be transported?
 
Not Applicable.
 
17.10 Who is responsible for receipt or transmission of the data or specimens?
 
Not Applicable.

--	--

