**TEMPLATE: RESEARCH PROTOCOL**

NUMBER	ACTIVE DATE	PAGE
HRP-503	02-04-2020	19 of 35

	Clinician Monitoring and Respiratory System Monitoring typically conducted by various surgical team members assigned for the patient's surgical procedure.
	18.3 How will the safety information will be collected?
	Safety information will be collected by the patient's surgical team in the charting conducted both pre and post operatively to coincide with UCMC's current standards of care for surgical procedures.
	18.4 The frequency or periodicity of review of cumulative data.
	The review will follow the duration of the surgical procedure and standard six-week follow-up provided by the patients care team.
	18.5 Who will review the data?
	Data will be reviewed by the surgical team members.
	18.6 The statistical tests for analyzing the safety data to determine whether harm is occurring.
Statistical testing will follow the outlined analysis for this current study as stated in the protocol.	
18.7 Any conditions that trigger an immediate suspension of research.	
The standard procedure is to not use a model, and thus we believe that looking at the model before the procedure is genuinely minimal risk. The surgeon will have already performed the review of the imaging (that forms the basis of the physical model), and therefore there is no risk of increased OR time for any patient. As we stated in the second to last paragraph of Page 3 in the initial submission, we are looking at potentially less time in the OR, as there will not be more time spent in the OR for any patient. This is looking to redefine the current standards of care minimizing the OR time already expected under the normal standards of care. No conditions would trigger immediate suspension as current standards of care will be utilized throughout surgery.	
19.1 Describe the provisions to protect participants' privacy and to minimize the intrusiveness of the study questions or procedures.	

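### The cost saving in Section 6.1 rests on minutes that 3D-arm surgeons felt were saved, so it cannot come out negative and makes no use of the randomised control arm

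*Protocol*

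**What the plan says.** Section 6.1 of the protocol says the study is to show whether the 3D models were "effective in minimizing both OR time and operational costs". After the operation, surgeons who had the model complete a Likert survey. Within it, "if they feel the model increased efficiency saving time, they will be asked to state how much time they felt was saved". The next sentence turns the answer into money: "This time differential will be compared to current CPT codes for OR time to understand how much in operational costs were saved". The only time quantity that this sentence can refer back to is the felt saving.

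Section 23.3 (consent of surgeons) confirms that the survey is answered only for procedures in which the surgeon was assigned the model.

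Elsewhere:
- Section 5.1 lists "Total time in the OR" and the time of the critical part of the procedure as Outcome 2. Section 1.2 states the hypothesis that both are shorter than in the control arm.
- Section 11.1 plans 50 procedures per arm.
- Section 17.5 lists "Cost differential via model utilization" as a data item without defining it, next to procedural time.
- Section 18.7 states that "there will not be more time spent in the OR for any patient".

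No section connects measured OR time in the two arms to cost.

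**The concern.** The cost input has three defects, and each favours the model or removes the protection of randomisation.

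1. **It is conditional on a favourable view.** Minutes are requested only from a surgeon who already believes time was saved. A surgeon who thinks the model cost 15 minutes has nowhere, in the procedure described, to record it.
2. **It comes from one arm.** No control-arm value enters. The surgeon is estimating how long the same case would have taken without the model, which nobody observed.
3. **It is gross.** Section 6.1 describes no subtraction of the cost of producing the model, although Section 2.1 introduces in-house printing as a question of cost as well as time.

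A trial randomised to learn whether the model saves time and money would then report a cost figure that cannot go against the model. The same report could show equal or longer measured OR time in the 3D arm beside a positive cost saving. Section 18.7 asserts in advance that no patient will spend longer in the OR. That is something the time comparison should test, and a cost rule that cannot register lost time in effect assumes it.

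**Working it through.** **The plan's own figure.** The protocol gives no projected cost saving, no OR-time SD and no calculation behind 50 per arm, so there is nothing to reproduce. What follows illustrates how the rule behaves.

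**Inputs.** From the protocol: 50 procedures per arm (Section 11.1), and minutes recorded only if a saving is felt (Section 6.1). Assumed: the perceived saving X in a 3D case is Normal with mean equal to the true mean saving μ (surgeons are right on average) and SD σ of 10, 20 or 30 min. The protocol does not say how cases that were not asked enter the average, so both options are shown.

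**Formulas** (Φ and φ are the standard Normal distribution function and density):
- Unasked cases counted as 0: E[max(X,0)] = μ·Φ(μ/σ) + σ·φ(μ/σ)
- Average among those asked: E[X | X>0] = E[max(X,0)] / Φ(μ/σ)

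**No true saving (μ = 0).** Here E[max(X,0)] = σ × 0.3989, and dividing by Φ(0) = 0.5 doubles it.

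| σ (min) | Unasked = 0, per case | Over 50 3D cases | Among those asked |
|---|---|---|---|
| 10 | 4.0 | 199 | 8.0 |
| 20 | 8.0 | 399 | 16.0 |
| 30 | 12.0 | 598 | 23.9 |

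**Small true effects (σ = 20).**
- True loss of 5 min: −5 × 0.4013 + 20 × 0.3867 = −2.0 + 7.7 = 5.7 min reported as saved; among those asked, 5.7/0.4013 = 14.3.
- True saving of 5 min: 5 × 0.5987 + 7.7 = 10.7 min, about double the truth; among those asked, 10.7/0.5987 = 17.9.

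**True loss of 10 min.** With unasked cases as 0, the rule still reports savings of 0.8, 4.0 and 7.6 min for σ = 10, 20 and 30.

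**Larger true savings (unasked = 0).** With μ = 20 the rule gives 20.1, 21.7 and 24.5 min for σ = 10, 20 and 30. With μ = 30 it gives 30.0 at σ = 10 and 30.6 at σ = 20. The upward bias fades when few surgeons would report a loss. With μ = 0 and no perception error (σ near 0) the rule gives 0.

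**What the randomised comparison would give.** With 50 per arm, SE = SD × √(2/50) = 0.2 × SD, and the 95% CI half-width is t(0.975, 98 df) × SE, with t = 1.98. For an assumed OR-time SD of 30 min the half-width is 1.98 × 6 = 11.9 min; for 60 min it is 1.98 × 12 = 23.8 min. This estimate can take either sign.

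**The case against.** The best defence is one of scope. Cost is not among Outcomes 1 to 3, the hypothesis in Section 1.2 concerns time only, and no listed endpoint depends on the felt minutes. That is correct and limits the severity. However, Section 6.1 declares cost an aim and Section 17.5 collects a cost differential, so a figure will be produced.

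A second argument is that Section 6.1 gives no formula, that the survey form is not shown, and that a net figure after deducting the cost of the model could be negative. All true. But the text as it stands fixes which minutes are used and when they are asked for, and it describes neither a deduction nor a way to record time lost. This is a method stated in the protocol, so it cannot be treated as a detail left to the SAP.

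Third, the size of the bias rests on assumed values and, as shown above, nearly vanishes if the true saving is large relative to the spread of surgeons' impressions. This stands, and the figures should not be read as an expected effect. The floor at zero and the absence of a control arm do not depend on those values.

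Fourth, the sentence in Section 18.7 answers a question about suspending the study, and the protocol does not tie it to costing. That link is an inference and the point does not rely on it.

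**Conclusion.** The point holds. Followed as written, Section 6.1 gives a cost saving that is subjective, drawn from one arm and bounded below by zero, although an unbiased measure of time in both randomised arms is already planned. With no true saving and an assumed perception SD of 10 to 30 min, the apparent saving is about 4 to 12 min per 3D case (unasked cases as 0) or 8 to 24 min among those asked. These sizes assume Normal, on-average-correct impressions. The direction of the bias is certain as long as some surgeons would have reported a loss. Outcome 2 is untouched and the damage is limited to the cost result, so this should be fixed but does not threaten the trial's listed outcomes.

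**What to change.** In Section 6.1, replace the sentence that compares the time differential with CPT codes by wording such as:

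> The cost difference per case is the signed between-arm difference (control minus 3D) in measured total OR time, with its 95% CI, multiplied by a stated OR cost per minute, minus the cost of producing the model.

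If the team wants CPT codes as the source of the price, it should state how they yield a cost per minute; the fault lies in the minutes used, not in the price. In Section 17.5, define the cost differential as this computed quantity.

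Keep the surgeon's estimate as descriptive only. Ask it of every 3D-arm surgeon as a signed number, with options for no change and for time lost. Make this change before the survey is used, because losses that were never asked about cannot be recovered reliably later.

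The cost is a wording change in two sections, a small change to the survey, and one new data item: the cost of the model per case. Section 2.1 gives $1,000 to $2,000 per case for outside services but no per-case figure for in-house models. OR time is already an outcome. The downside is that the reported saving may be smaller or negative, and its interval will be wide: about ±12 to ±24 min before conversion to cost, at assumed OR-time SDs of 30 to 60 min.

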**TEMPLATE: RESEARCH PROTOCOL**

NUMBER	ACTIVE DATE	PAGE
HRP-503	02-04-2020	8 of 35

**example, please be sure that what will be done for this research is explained and differentiated from activities that have already taken place or will be submitted for future review. Please note that details about recruitment and consent are asked in later questions.**

The primary goals in the management of mandibular fractures are restoration of functional occlusion and facial form. There are frequently several appropriate techniques available for the definitive management of a given mandible fracture. In general, mandible fractures are treated either closed (maxillomandibular fixation, splinting, modified diet) or open (plates and screws, interosseous wiring, lag screws). The technique chosen depends on several variables including, dental status, fracture characteristics (open, closed, favorable, unfavorable, comminution, bone lose, mechanism of injury, contamination, or frank infection etc.), fracture location, associated injuries, patient mental status and patient desires. The most important considerations are the dental status, fracture characteristics and fracture location.

The main surgical techniques that will be performed will be as follows:

Open reduction and internal fixation of mandible fractures is an evolving science. There are several different techniques used to internally fixate mandible fractures. Simple interosseous wiring to supplement intermaxillary fixation is a form of open reduction and internal fixation. There are a variety of plate and screw systems available for the repair of mandible fractures. Compression plating of mandibles has become popular over the last 10 years. Compression plate fixation allows direct bone healing and, in most cases, eliminates the need for 4 to 6 weeks of maxillomandibular fixation needed with closed reduction techniques. Compression plates used on the inferior cortex must always be used with some form of tension band as discussed above. A special type of compression plate called an eccentric dynamic compression plate can be used without a tension band. This plate has sliding ramp holes which allow compression of the fracture not only in the plate but also at the tension side of the mandible. In general, the application of compression plates requires that the angle of the fracture be no more than 30 degrees from a line perpendicular to the long axis of the plate. If an angle greater than this exists, the compression plate will cause the fragments to slide against one another rendering the reduction nonanatomic and not in compression.

If internal fixation is desired and compression plating cannot be performed due to an oblique fracture or significant comminution of fragments, several other options exist. Reconstruction plates are large plates which use at least three screws on each side of the fracture. They hold the bone in absolute stability and because of their large size and stability, they do not require a tension band. Reconstruction plates are useful in cases of severely comminuted mandible fractures such as those resulting from gunshot injuries. If correctly placed small, no compression plates (called adaptation plates) may be used to repair mandible fractures. The most well-known of these systems is the Champy system. One final method of internal fixation of mandible fractures is with lag screws. A lag screw can compress two bone fragments and therefore permits direct bone healing. The number of fracture cases suitable

NUMBER	ACTIVE DATE	PAGE
HRP-503	02-04-2020	9 of 35

for lag screw repair is relatively small and this technique requires considerable experience and skill.

Fractures of the mandible can be approached either trans orally or through the neck. In closed fractures one advantage of approaching the fracture through the neck is the absence of salivary contamination of the wound. The obvious drawback in an external approach is a scar. Most symphyseal and body fractures can be easily plated through the mouth. Angle and ramus fractures are difficult to approach through the mouth and if an intraoral approach is performed special instruments for the transcutaneous placement of screws must be available. Patients with open mandible fractures should be on antibiotics active against oral cavity organisms including anaerobes. Perioperative antibiotics have been shown to decrease the rate of wound infections.

